5.2.4. Exploratory

Exploratory endpoints will not be included in this SAP.

5.2.5. Sub-Group Analyses

The primary analysis and each of the secondary analyses will be conducted in different patient subgroups of the mITT population for exploration of heterogeneity of treatment effect. The following patient subgroups will be analyzed when sufficient data are available (i.e. if a listed group makes up at least 20% of the analysis population):

- Age: <30 years, 30-50 years, >50 years
- Sex: Female, Male
- SARS-Cov-2 vaccination status
- Location (country): Thailand, USA, South Africa

5.2.6. Adverse events

An adverse event is any untoward medical occurrence associated with the use of an intervention in humans, regardless of whether the event is considered intervention-related or not. All adverse events that occur from the first dose of study medication through Week 12 after enrollment must be recorded.

AEs will be coded using MedDRA, version 24.0 or higher; AE severities will be graded using the Grading the Severity of Adult and Pediatric Adverse Events (DAIDS AE Grading Table), corrected Version 2.1, July 2017.

A treatment-emergent adverse event is defined as any event not present prior to the initiation of the IP or any event already present that worsens in either intensity or frequency following exposure to the IP.

An adverse event (AE) or suspected adverse reaction is considered "serious" if, in the view of either the investigator, medical monitor, or sponsor, it results in any of the following outcomes:

- Death
- A life-threatening adverse event
- Inpatient hospitalization or prolongation of existing hospitalization
- A persistent or significant incapacity or substantial disruption of the ability to conduct normal life functions
- A congenital anomaly/birth defect
- Important medical events that may not result in death, be life-threatening, or require hospitalization may be considered serious when, based upon appropriate medical judgment, they may jeopardize the participant and may require medical or surgical intervention to prevent one of the outcomes listed in this definition

Adverse events can be classified as/by:

- Investigational Product-related or not Investigational Product-related.
 - Relationships reported as definitely, probably, or possibly related are considered related to IP;
 - Relationships reported as unlikely or unrelated are considered not related to IP.
- Severity of Event

For AE not included in the protocol-defined grading system, the following guidelines will be used to describe severity:

- Grade 1 (Mild) – Mild symptoms causing no or minimal interference with usual social & functional activities with intervention not indicated.
- Grade 2 (Moderate) – Moderate symptoms causing greater than minimal interference with usual social & functional activities with intervention indicated
- Grade 3 (Severe) – Severe symptoms causing inability to perform usual social & functional activities with intervention or hospitalization indicated.
- Grade 4 (Life-threatening) – Potentially life-threatening symptoms causing inability to perform basic self-care functions with intervention indicated to prevent permanent impairment, persistent disability
- Grade 5 (Death)

Safety analyses will include

- Incidence of Serious Adverse Events
- Adverse Events
- Adverse Events \geq Grade 3
- IP discontinuation due to AE
- All-cause IP discontinuation
- Hospitalization due to any adverse events

The number and percentage of participants with AEs will be summarized for each treatment group. Overall treatment group differences may be compared using Chi-square tests or Fisher's exact tests.

Serious AE and hypersensitivity reactions will also be summarized. The counts and proportion of participants experiencing these events will be reported for each treatment arm. Treatment groups may be compared by Chi-square tests or Fisher's exact tests.

Permanent discontinuations or interruptions of upamostat due to AEs will be listed. The count and proportion of discontinuations of the study drug due to AEs will be reported.

Categorical safety measures (e.g. hospitalization) will be summarized with counts and proportions of participants and may be compared by treatment using either a Chi-square test or a Fisher's exact test.

All AE will be summarized by worst DAIDS grade and presented by System Organ Class (SOC), Preferred Term (PT), and treatment group, as follows.

- All AE
- All Related AE
- All AE leading to study drug discontinuation
- All SAE

All AE data will be provided in listings. A listing of any on-study deaths will be presented.

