 - Electrocardiographic evidence of complete LBBB, RBBB, incomplete LBBB, in complete RBBB
 - Evidence of second- or third-degree heart block
 - Intraventricular conduction delay with QRS duration > 120 msec
 - Bradycardia as defined by sinus rate < 50 bpm
 - Personal or family history of long QT syndrome
 - Personal history of cardiac disease, symptomatic or asymptomatic arrhythmias, except for sinus arrhythmia
 - Syncopal episodes or additional risk factors for torsades de points (e.g., heart failure, hypokalemia)

C 6.3 Lifestyle Considerations

Lifestyle Considerations as specified in the Master Protocol and:

- 1. Participants that engage in sexual activity that may lead to pregnancy in their partner must agree to either remain abstinent or use male contraceptives. They are also strongly advised to inform their non-pregnant sexual partners of reproductive potential to use effective contraceptives for 8 weeks after investigational agent is administered.**
- 2. Participants should refrain from sperm donation for 8 weeks after investigational agent administration.**
- 3. Upamostat may increase the sedative effects of alcohol so participants are encouraged to avoid alcohol while taking the study medication.**

C 7 STUDY INTERVENTION

C 7.1.1 Study Intervention Description

Upamostat is designated chemically as ethyl 4-{3-[(E)-amino(hydroxyimino)methyl]-N-[(2,4,6-triisopropylphenyl) sulfonyl]-L-phenylalanyl}-piperazine-1-carboxylate hydrogen sulphate.

C 7.1.2 Dosing and Administration

Upamostat 400 mg will be dosed orally once daily for 14 days.

C 7.2 Preparation/Handling/Storage/Accountability

C 7.2.2 Acquisition

Upamostat and placebo will be provided by RedHill either directly or through a third-party clinical supply distributor.

C 7.2.4 Formulation, Appearance, Packaging, and Labeling

Size 1 oral capsules contain a white to yellowish powder of 200 mg upamostat or placebo and are packaged in round white, 40 cc 33-400 wide-mouth marlex bottles with a white 33mm child resistant polypropylene cap with an induction seal at 30 capsules per bottle.

A standard label will be adhered to each bottle. Participants will be assigned to receive their treatment according to the randomization. For each cohort, randomized subjects will be assigned a unique number.

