- Comparison between active and placebo treatment groups in proportion of all and \geq grade 3 adverse events as assessed by the National Institutes of Health, Division of AIDS Table for Grading the Severity of Adult and Pediatric Adverse Events (DAIDS AE Grading Table), corrected Version 2.1, July 2017.
- Incidence of AEs causing IP discontinuation
- Incidence of all-cause IP discontinuation or interruption
- Number of participants hospitalized due to adverse events regardless of cause

All adverse events will be listed by participant and will include:

- Event description
- Treatment group (active agent vs placebo)
- Clinician's assessment of severity and relationship to upamostat
- Outcome

The number and percentage of participants with AEs will be summarized for each treatment group. Overall treatment group differences may be compared using Chi-square tests or Fisher's exact tests.

Serious AEs, TEAEs, and hypersensitivity reactions will also be summarized. The counts and proportion of participants experiencing these events will be reported for each treatment arm. Treatment groups may be compared by Chi-square tests or Fisher's exact tests.

Permanent discontinuations or interruptions of upamostat due to AEs will be listed. The count and proportion of discontinuations of the study drug due to AEs will be reported.

Categorical safety measures including hospitalization will be summarized with counts and proportions of participants and may be compared by treatment using either a Chi-square test or a Fisher's exact test.

C 13.5.1.4 Exploratory

Prevalence and titer of anti-SARS-CoV-2 IgM and IgG antibodies at baseline and at Week 8 will be determined, and the effect of presence and titer of anti-SARS-CoV-2 IgG at baseline on treatment outcome will be assessed.

For participants receiving upamostat, targeted analysis of known host transmembrane protease polymorphisms will be described and compared to time to resolution of symptoms among key subgroups including by sex, race, and ethnicity.

C 13.5.1.5 Sub-Group Analyses

The primary analysis and each of the secondary analyses will be conducted in different patient subgroups of the mITT population for exploration of heterogeneity of treatment effect. The following patient subgroups will be analyzed:

- Age (< 30, 30-50, >50 years old)
- Sex
- Race
- Baseline symptom severity
- SARS-CoV-2 vaccination status
- Location (by continent)

C 13.6 Interim Analysis Plan

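### The SAP pools adverse events over 12 weeks for a drug dosed for 14 days, and its treatment-emergent definition has no end and feeds no table; an added fixed-window table is a cheap improvement.

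*SAP*

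**What the plan says.** Protocol C 7.1.2 sets the treatment course: "Upamostat 400 mg will be dosed orally once daily for 14 days". SAP 5.2.6 sets the AE recording period: "All adverse events that occur from the first dose of study medication through Week 12 after enrollment must be recorded".

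The same SAP section opens its TEAE definition with "A treatment-emergent adverse event is defined as any event not present prior to the initiation of the IP" and extends it to existing events that worsen after exposure. It gives no last day. The outputs that follow are all AEs, AEs of Grade 3 or higher, SAEs, related AEs, AEs leading to discontinuation, all-cause discontinuation, and hospitalization for AEs. None refers to the TEAE definition or restricts onset to a period around dosing. On testing, the section says only "Overall treatment group differences may be compared using Chi-square tests" or Fisher's exact test.

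Protocol C 13.5.1.3 planned more: "Serious AEs, TEAEs, and hypersensitivity reactions will also be summarized". The matching SAP sentence reads "Serious AE and hypersensitivity reactions will also be summarized". SAP Appendix A is where changes are to be documented. Its four entries cover exploratory endpoints, references to other product arms, the interim analysis and events of special interest. The TEAE summary is not among them.

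**The concern.** The comparison between arms of all AEs and of Grade 3 or higher AEs is a stated safety endpoint (protocol C 4.1, SAP 3.4). A participant counts as having an AE whether it begins on Day 2 or in Week 11. Events late in follow-up that have nothing to do with a 14-day course raise the proportion in both arms and pull the risk difference toward zero. In a safety analysis that is the less cautious direction.

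A TEAE analysis is the usual protection, but here it would not help as defined. Recording starts at first dose, so with no end to the window the TEAE set and the all-AE set nearly coincide. Restoring the protocol's TEAE table unchanged would add almost nothing. The missing end of the window is the defect; the unlogged omission is a smaller one beside it.

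**Working it through.** **Plan's own figure.** The documents state no power and no assumed rate for the AE comparison. Their power figures concern the primary endpoint and do not bear on this point.

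**Windows.** 12 weeks = 84 days; 14/84 = 16.7%.

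**Dilution.** Let p0 and p1 be the proportions with an AE in the on-treatment window (placebo, upamostat). Let q be the proportion with a first AE after it, among those with none in it, assumed equal in both arms. Each 12-week proportion is

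P = 1 − (1 − p)(1 − q),

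so P1 − P0 = (1 − q)(p1 − p0). The shrinkage applies to the estimate and its interval as well as to any test.

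**Power.** Two proportions, two-sided 5%, n per arm, pooled standard error under the null:

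power = Φ{[(P1 − P0) − 1.96·SE0] / SE1}, with SE0 = √[2·P̄(1 − P̄)/n], SE1 = √[(P0(1 − P0) + P1(1 − P1))/n] and P̄ = (P0 + P1)/2.

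The 5% level is borrowed from SAP 5.2, which concerns efficacy. The 150 per arm is the planned size in protocol C 13.9. All AE rates in the table are assumptions.

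Worked case, 30% vs 45%, n = 150:
- q = 0: difference 0.15, SE0 = 0.0559, SE1 = 0.0552; (0.15 − 0.1096)/0.0552 = 0.732; power 0.768.
- q = 20%: P0 = 1 − 0.70×0.80 = 0.44 and P1 = 1 − 0.55×0.80 = 0.56; difference 0.12, SE0 = 0.0577, SE1 = 0.0573; (0.12 − 0.1132)/0.0573 = 0.119; power 0.548.

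| Assumed on-treatment rates | n per arm | q = 0 | 10% | 20% | 30% | 40% |
|---|---|---|---|---|---|---|
| 30% vs 45% | 150 | 0.768 | 0.656 | 0.548 | 0.449 | 0.363 |
| 10% vs 25% | 150 | 0.932 | 0.765 | 0.593 | 0.452 | 0.344 |
| 2% vs 8% | 150 | 0.666 | 0.263 | 0.162 | 0.117 | 0.092 |
| 30% vs 45% | 75 | 0.475 | 0.384 | 0.311 | 0.252 | 0.205 |
| 10% vs 25% | 75 | 0.680 | 0.472 | 0.340 | 0.254 | 0.195 |

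Exact Fisher power for 30% vs 45% at 150 per arm follows the same course: 0.730, 0.628, 0.524, 0.420 and 0.319.

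**How scenario-dependent this is.** At 150 per arm, power halves at q of about 37% for 30% vs 45%, but at about 7% for 2% vs 8%. For a contrast as large as the pilot's INR/aPTT increases (25% placebo vs 62% at 400 mg in protocol C 3.4.1.1; C 5.4 gives 65%), power is still 0.949 at q = 50% and halves only at about 81%.

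**The case against.** **Halved power is not a finding.** A reader might infer that the 12-week window halves the chance of seeing a drug effect. Nothing in the documents establishes that. They give no AE rate after Day 14 and no on-treatment rates for this trial. The pilot clinical AE rates in protocol C 5.4 (Grade 1, Grade 2) are 10% and 20% on placebo and 19% and 10% on 400 mg. If the grades are exclusive, that is about 30% vs 29%, which is no excess to mask. This part of the objection stands.

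**Not every AE output is diluted.** Discontinuation of study drug can happen only while dosing continues. The "All Related AE" table screens out the events judged unrelated. Laboratory values, including aPTT and INR, and QTcF are summarized by visit, so their timing is visible. AEs are also tabulated by System Organ Class and Preferred Term, and late unrelated events spread over many terms, so a large q for any AE does not carry over to a single term. This also stands. It does not remove the point, because the related-AE table rests on investigator attribution and the by-visit summaries do not show clinical events.

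**Equal late rates are a modelling assumption.** Protocol C 12.1 follows some coagulation abnormalities as far as Week 8, so the period after dosing is not treated as irrelevant to safety. A reader might conclude that a short window should replace the 12-week comparison. The documents do not support that: the protocol's endpoint is all AEs, and late harm must stay in view.

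**The tests are optional and unpowered.** Enrollment ended before the interim trigger (SAP Appendix A), and the final size is not stated. At 75 per arm, 30% vs 45% has power of only 0.475 with no late events at all, so sample size matters more than the window. That limits the severity, but not the shrinkage of the estimate.

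**The Master Protocol is not among the documents.** An AE window defined there cannot be checked.

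**Conclusion.** The point holds as a minor one. Three facts rest on the text alone: AEs are pooled over 84 days for a 14-day course; the TEAE definition has no end and no listed output uses it; and the protocol's TEAE summary is missing from the SAP without a log entry. The (1−q) shrinkage follows by arithmetic once late unrelated events are taken as equally frequent in both arms. It applies to the all-cause and Grade 3 or higher comparisons.

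The loss of power is conditional. For 30% vs 45% at 150 per arm, q of 10% to 20% costs about 15% to 29% of the power (0.656/0.768 and 0.548/0.768). Rarer events lose more, and a large contrast loses little. A reader might go further and suppose that the plan hides a drug harm. The documents show neither such a harm nor a late AE rate, and several planned outputs would reveal one by other routes.

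**What to change.** In SAP 5.2.6, before unblinding:

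1. Give the TEAE definition an end: onset from first dose through last dose plus a fixed number of days chosen by the sponsor.
2. Restore the TEAE summary as an added between-arm table for all AEs and for Grade 3 or higher AEs in that window. Show the difference of proportions with a 95% confidence interval, as SAP 4.8 already does for binary endpoints.
3. Keep the all-AE and SAE summaries and the reporting of deaths through Week 12, so that the protocol's endpoint is unchanged and late events stay visible.
4. Record in Appendix A the earlier omission of the TEAE summary, the new definition, and their timing relative to unblinding.

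The cost is one extra set of tables. It needs only AE onset dates and dosing dates, and no new data collection.

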5.2.7. Electrocardiogram

Observed and changes from baseline QTc Fridericia (QTcF) interval data will be summarized by treatment group, cohort and scheduled visit. A listing of all results will be provided.

QTcF will be calculated as

$$QTc = \frac{QT}{RR^{1/3}}$$

where QT is the QT interval duration and RR is the interval between R waves.

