The administration of IP to any participant may be stopped or paused for any SAE, clinically significant AE, severe lab abnormality or any medical condition that may indicate to the Investigators that IP continuation is not in the best interest of the participant. In addition, a subject in the clinical trial may discontinue study drug at their request for any reason. Every effort should be made to encourage subjects to remain in the study for the duration of their planned outcome assessments. Unless the subject withdraws the consent, those who discontinue study drug early will remain in the study. The reason for subject discontinuation will be documented in the case report form.

For an individual participant, the 14-day course of IP can be interrupted or stopped if there is a suspected drug-related event suggestive of QTc interval prolongation, anticoagulant effect, elevated liver enzymes or other, as per investigator or medical monitor discretion if it is deemed to be in the participant's best interest. All participants will receive baseline chemistry, liver enzyme, and coagulation studies as well as a baseline ECG.

The individual pause and stopping criteria will include (but not be limited to) the following:

- The subject worsens and requires treatment for worsening COVID-19 as recommended by the NIH COVID-19 Treatment Guidelines. Upamostat administration will be discontinued. All other study activities will continue, participant will not be withdrawn from the study.
- The subject worsens and requires hospitalization for worsening COVID-19. Upamostat administration will be discontinued. All other study activities will continue, participant will not be withdrawn from the study.
- QTc Interval: QTc increase >60 msec over baseline: repeat ECG within 48 hours and if >60 msec increase over baseline persists, IP will be discontinued. Participant will continue to be participate in follow up visits and, if necessary, until resolution or stabilization of the event.

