- INR, PTT: increase over baseline > 2 Grades (per NIH DAIDS Table for Grading the Severity of Adult and Pediatric Adverse Events (DAIDS AE Grading Table) corrected Version 2.1, July 2017): pause therapy. Repeat INR and PTT within 48 hours of initial awareness of the abnormal laboratory value. If repeat testing \leq 2 Grades above baseline, may resume therapy until total of 14 days from start; missed days will not be made up. If repeat testing > 2 Grades above baseline, IP will be discontinued. Participant will continue to be participate in follow up visits and, if necessary, until resolution or stabilization of the event.
 - If increase over baseline 1 Grade: no additional follow up
 - If increase over baseline 2 Grades: In addition to scheduled PTT/INR testing on Day 3 and Day 14, participant will have coagulation testing on Day 28. If either PTT or INR is increased by \geq 1 Grade at Day 28, repeat testing will be performed at Week 8. Additionally, participant will be questioned at Day 7, Day 10, Day 14 visits, and

twice weekly from Day 14 until resolution of the coagulation abnormality to ≤ 1 Grade above baseline or Week 8 (whichever comes first), regarding bleeding, bruising or petechiae.

- Transaminases, bilirubin: increase over baseline >1 Grade above baseline: pause therapy. Repeat transaminase and bilirubin levels within 48 hours of initial awareness of the abnormal laboratory value. If repeat testing ≤ 1 Grade above baseline, may resume therapy until total of 14 days from start; missed days will not be made up. If repeat testing >1 Grade above baseline, IP will be discontinued. Participant will continue to be participate in follow up visits and, if necessary, until resolution or stabilization of the event.

C 12.2 Study and/or PSA Pause and Stopping Criteria

In addition to those listed in the Master Protocol, the study pause criteria listed in Table 1 will apply.

Table 1 Product Specific Criteria for Study Pause

Parameter	Investigational Products Related Adverse Events (AEs)	Action
Prolonged QTc Interval	QTc ^a >500 msec OR QTc ^a >60 msec above baseline on repeat ECG within 48 hours	Prompt reporting (within 24 hours of observation or report) Consider pause of the PSA PSRT to monitor for trend
ALT (SGPT), ALP (SGOT), or Total Bilirubin, High	> 1 Grade ^c increase in verified ^d abnormal AST, ALT, and total bilirubin in >2 patients	Prompt reporting (within 24 hours of observation or report) Consider pause of the PSA PSRT to Monitor for trend

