PT, PTT, or INR, High (Not on anticoagulation therapy)	> 2 Grade increase in verified PT, PTT or INR >2 patients	Prompt reporting (within 24 hours of observation or report) Consider pause of the PSA PSRT to Monitor for trend

a Corrected QT may be calculated using any standardized formula or automated interpretation. The same methodology for calculating the QT interval should be applied throughout the participants enrollment in the study

c Per NIH DAIDS Table for Grading the Severity of Adult and Pediatric Adverse Events (DAIDS AE Grading Table) corrected Version 2.1, July 2017

d Verified definition: If no evidence of disease is present other than the abnormal laboratory value, the test must be repeated at least one time in order to be considered “verified”. The verification period will be a maximum of 48 hours after initial awareness of the abnormal laboratory value. When signs and symptoms are present, repeat test WILL NOT be needed

C 13 STATISTICAL CONSIDERATIONS

C13.1 Statistical Hypotheses

The primary hypothesis is that early treatment with upamostat among outpatients infected with SARS-CoV-2 can shorten time to sustained alleviation or resolution of Targeted COVID-19 symptoms (time to resolution) as compared to standard treatment.

The general statistical approach will compare outcomes among participants randomized to receive the active agent, upamostat, to outcomes among participants who were eligible to have been randomized to upamostat but who were randomized instead to any of the placebo arms enrolling at that time. This ensures that the comparison is limited to concurrently randomized participants eligible to receive upamostat.

C 13.4 Primary Endpoint/Estimand Analysis

The primary objective is to estimate the relative time to sustained alleviation or resolution of symptomatic COVID-19 infection for a participant that receives upamostat compared to a participant that does not receive upamostat.

The estimand of interest is the hazard ratio of a participant that has symptomatic COVID-19 with standard of care background therapy when starting treatment with upamostat compared to no upamostat. A hazard ratio greater than 1 indicates a shorter time to resolution of symptomatic COVID-19 infection.

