4.8. General Issues

General descriptive statistics for numeric variables include

- Continuous variables: mean, standard deviation, percentiles (median, 25th, 75th), minimum, maximum

- Categorical variables: frequency, percentage calculated based on subjects with reported values (i.e., subjects with missing data will not contribute to denominators of percentages)

Descriptive statistics and tabular summaries will be presented by treatment group.

For binary endpoints, proportion of participants with the event will be summarized by treatment group. Comparison between groups will be presented as the difference of proportions with its 95% confidence interval. For categorical endpoints, proportion of participants in each category will be summarized by treatment group

Unless otherwise specified, the following guidelines will be followed when displaying statistics:

- measures of central tendency and percentiles will be displayed with one decimal place more than the raw (collected) data
- measures of variability will be displayed with two decimal places more than the raw (collected) data
- percentages will be displayed with one decimal place
- 1 year = 365.25 days. Number of years is calculated as (days/365.25) rounded up to 1 significant digit.
- 1 month = 30.4375 days. Number of months is calculated as (days/30.4375) rounded up to 1 significant digit.
- For laboratory results collected as < or >, a numeric value, 0.0000000001 will be subtracted or added, respectively, to the value.
- For by-visit observed data analyses, percentages will be calculated based on the number of patients with non-missing data as the denominator.

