5.2.8. Safety Laboratory

Observed and changes from baseline in laboratory values will be summarized by treatment group and scheduled visit. Safety laboratory parameters to be summarized include complete blood count (hemoglobin, platelets, leukocytes), differential (absolute counts of basophils, eosinophils, lymphocytes, monocytes, total neutrophils), renal/liver (BUN, creatinine, alanine

aminotransferase, aspartate aminotransferase, total bilirubin, direct bilirubin, total protein), and coagulation (aPTT, INR).

Laboratory abnormalities considered clinically significant will be entered by the investigators as adverse events and graded, classified by causality and included in the AE listings and tables accordingly.

By-subject listings will be provided for laboratory parameters of blood chemistry, hematology, and coagulation studies. Laboratory values outside the corresponding normal ranges will be flagged in listings.

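### SAP 5.2.7 plans no by-arm count of participants whose QTcF crosses the protocol's action limits; one descriptive table and a listing flag would supply it

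*SAP*

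**What the plan says.** SAP 5.2.7 recalculates QTc by Fridericia's formula and plans this: "Observed and changes from baseline QTc Fridericia (QTcF) interval data will be summarized by treatment group, cohort and scheduled visit". A listing of every result follows, with no flagging rule. SAP 4.8 defines the summary: "Continuous variables: mean, standard deviation, percentiles (median, 25th, 75th), minimum, maximum".

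The protocol sets limits for the individual participant. Under C 12.1, a QTc rise above 60 msec leads to this instruction: "repeat ECG within 48 hours and if >60 msec increase over baseline persists, IP will be discontinued". Under C 12.2, Table 1, a pause of the product arm is considered at QTc above 500 msec, or at more than 60 "msec above baseline on repeat ECG within 48 hours". Table 1 places both under a column for product-related adverse events and asks for reporting within 24 hours. Its footnote a leaves the formula to the site: "Corrected QT may be calculated using any standardized formula or automated interpretation". The only constraint is that the method stays the same for a given participant.

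Two other SAP sections bear on the point. On adverse events, 5.2.6 says: "The count and proportion of discontinuations of the study drug due to AEs will be reported". On laboratory data, 5.2.8 says: "Laboratory values outside the corresponding normal ranges will be flagged in listings". Section 5.2.7 has no counterpart to that flag.

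**The concern.** The protocol treats QT prolongation as a matter for individual action. It excludes people with QTc above 450 msec or conduction abnormalities, schedules ECGs at baseline, Day 3 and Day 14, and sets a stopping limit and a pause limit. The SAP then reports QTcF only as a distribution at each visit. A limit that applies to individuals is most directly compared between arms as the number of participants who crossed it, and the SAP's safety objective (3.4) is a comparison of upamostat with control.

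The adverse-event route does produce counts by arm, but of a different quantity: crossings that a site recognised with its own formula and then reported or acted on. The SAP already has one formula for everyone and never applies the limits to it. At stake is whether the report can state, on one definition, how many participants in each arm crossed a limit.

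**Working it through.** The plan states no figure on this point, so there is none to reproduce. The check sets the outputs side by side and then tests two things: whether site formulas can disagree with QTcF, and how far the by-visit statistics fix the count.

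**1. What each planned output delivers**

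| Output | Formula | Includes repeat ECGs? | Count by arm of crossings? |
|---|---|---|---|
| By-visit QTcF summary (SAP 5.2.7, 4.8) | Fridericia | No, scheduled visits only | No |
| ECG listing (SAP 5.2.7) | Fridericia | Yes, it covers all results | No; hand count only, values unflagged |
| AE tables (SAP 5.2.6) | Site's choice | If the site reports the event | Reported events, by term and grade |
| Discontinuations (SAP 5.1.1, 5.2.6) | Site's choice | If the site stops treatment | Stops only |

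No row combines the uniform formula, all ECGs and a count by arm.

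**2. Can the site's formula and QTcF disagree?** Take Bazett's formula as the example. That choice and the heart rates (HR) are assumptions; the documents give neither.

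- Fridericia (SAP 5.2.7): QT/RR^(1/3). Bazett: QT/RR^(1/2). With RR = 60/HR, Bazett = Fridericia × (HR/60)^(1/6).
- The factor is 1.0260 at 70 bpm and 1.0699 at 90 bpm.
- QTcF 400 to 465 (+65), HR 90 to 70: Bazett 428.0 to 477.1, a rise of 49. The site sees no crossing.
- The same QTcF rise at a constant 70: 410.4 to 477.1, a rise of 67. Both formulas agree.
- The same QTcF rise, HR 70 to 90: 410.4 to 497.5, a rise of 87.
- QTcF 400 to 445 (+45), HR 70 to 90: 410.4 to 476.1, a rise of 66. The site acts on a rise that is not a QTcF crossing.
- For the absolute limit, QTcF 480 at 90 bpm is 513.6 by Bazett, above 500 on one formula only.

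The two counts can therefore differ in either direction.

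**3. How far do the by-visit statistics fix the count?** Arm size is assumed to be 75. SAP Appendix A says enrollment ended before the interim trigger, and protocol Table 2 sets that trigger at 75 upamostat participants through Day 28.

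- The maximum shows whether at least one scheduled change exceeded +60.
- With mean change near 0 and SD s, the one-sided Chebyshev inequality bounds the number at or above +60: k ≤ 75 × s²/(s² + 60²).
- s = 15 (assumed): 75 × 225/3825 = 4.4, so at most 4.
- s = 20 (assumed): 75 × 400/4000 = 7.5, so at most 7.
- The SD carries real information. With everyone else at zero change, 1 participant at +65 gives mean 65/75 = 0.9 and SD 7.5; 5 participants give mean 325/75 = 4.3 and SD 16.3. Real data have background scatter, so these figures bound the count without giving it.
- Separate tables for Day 3 and Day 14 do not show whether the same participant crossed at both.

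**4. Would a test help?** A split of 5 of 75 against 0 of 75, chosen only for illustration, gives a two-sided Fisher p of 0.058. The count is useful as description, not for inference.

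**The case against.** The strongest reply is that nothing promised is missing. The limits are operational stop and pause rules, and no safety endpoint in the protocol or SAP mentions QTc. Because footnote a lets the site choose the formula, the events the protocol acts on are site-formula crossings, and those do reach the adverse-event and discontinuation tables. A QTcF count is a new derived measure. All of this stands. A reader might infer that the SAP drops an analysis the protocol requires, or that QTc crossings are counted nowhere. The documents support neither reading.

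A second reply is that most of the information is already there: two scheduled post-baseline ECGs per participant, the maximum by arm and visit, and a complete listing on one formula. That stands too. What remains is that the count has to be made by hand from unflagged values. The SAP 5.2.6 sentence on categorical safety measures does not fill the gap, since its only example is hospitalization and no QTc category is defined.

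A third concerns size. A reader might use the maximum and upper quartile alone and infer that nearly a quarter of an arm could have crossed unseen. That ignores the planned SD: with a mean change near zero, 18 of 75 at or above +60 would need an SD of about 34 msec (60 × √(0.24/0.76) = 33.7).

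Finally, the examples are hypothetical. No document says that a site uses Bazett, and the upamostat risks described in the protocol include no QTc effect. The examples show that disagreement is possible, not that it occurred.

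**Conclusion.** The point holds as a low-severity improvement to safety reporting. No planned by-arm output counts participants above the limits on the SAP's uniform QTcF, and the repeat ECGs that confirm a rise are outside the by-visit summary. The planned statistics narrow the possible count, to about 4 to 7 at most under the stated assumptions, without reporting it.

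It would be wrong to infer that participants are less well protected. Reporting within 24 hours, the individual stopping rule and DSMB review do not depend on this table. No primary conclusion changes.

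The conclusion rests on the SAP and Appendix C alone; the Master Protocol and DSMB Charter were not available. The sizes rest on an inferred arm of about 75, assumed SDs and assumed heart rates. The textual gap rests on none of these.

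**What to change.** Add to SAP 5.2.7, for the Safety Population, a table of n (%) by arm with:

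- worst post-baseline QTcF above 500 msec;
- worst QTcF increase from baseline above 60 msec;
- of those increases, the number confirmed on a repeat ECG, shown separately.

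Use scheduled, unscheduled and repeat ECGs, with the baseline already defined in SAP 4.10. Make the table descriptive, with no test and no confidence interval. Label it as a QTcF-based count that may differ from the site-formula stopping events. Keep the by-visit summary, and flag these values in the ECG listing as 5.2.8 does for laboratory values.

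The cost is a few lines of SAP wording, one table and one listing flag, from ECG data already collected and listed. If the SAP is not reopened, the addition can be documented in the clinical study report, as SAP section 1 provides for changes to the planned analysis.
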